### 12.2 Objectives:

The primary efficacy objectives are:

- Assess the non-inferiority of chronic VLU closure at 16 weeks with ACTitouch® therapy compared to a standard regimen of multi-layer bandaging.

The secondary and exploratory efficacy objectives include assessment of the effect of ACTitouch® compared with multi-layer bandaging treated subjects on:

- HRQOL
- outpatient cost per patient
- incidence of 100% healed VLU
- ulcer free days
- outpatient cost per patient healed
- outpatient cost per patient not healed
- time-to-100% healed
- cumulative incidence of 100% healed
- total cost per patient (including inpatient costs)

The safety objective is to compare ACTitouch® treated subjects to multi-layer bandaging treated subjects at 16 weeks in terms of the incidence of ulcer-related adverse events including infections, maceration, allergic reaction to dressing, hospitalization for worsening VLU.

### 12.3 Endpoints:

#### 12.3.1 Primary Endpoints

The percentage of ulcer area reduction at 16 weeks.

#### 12.3.2 econdary Endpoints

The secondary endpoints in clinical order of prioritization are as follows:

- the difference in changes in HRQOL at 16 weeks using the overall score of the Charing Cross Venous Ulcer Questionnaire.
- outpatient cost per subject at 16 weeks

#### 12.3.3 xploratory Endpoints

- the incidence of subjects with 100% healed VLUs at 16 weeks
- ulcer-free days at 16 weeks
- HRQOL at 16 weeks using the overall and physical scores of the SF-36.
- outpatient cost per subject for subjects with 100% healed VLU at 16 weeks
- outpatient cost per subject for subjects without 100% healed VLU at 16 weeks
- time-to-100% healed VLU
- cumulative incident of 100% healed
- total cost per patient (including inpatient costs)
- ease of use
- treatment satisfaction
- limb volume changes
- compliance

#### 12.3.4 Safety Endpoints

The safety endpoints are as follows:

- the incidence of ulcer-related adverse events at 16 weeks
- the incidence of ulcer infections at 16 weeks
- the incidence of hospitalization for worsening VLU at 16 weeks

#### 12.4 Sample Size Assumptions:

#### 12.5 Analysis Populations:

**Intent-to-Treat (ITT):** All randomized subjects.

**Modified-intent-to-treat (MITT):** All randomized subjects who received the investigational procedure per protocol. This is the primary analysis population.

**Per-Protocol (Completers):** All randomized subjects who have received the investigational procedure per protocol and who completed the 16 week follow-up visit.

The Primary and Secondary Efficacy analyses will be performed on the ITT, MITT and Completer populations. Safety analyses will be performed on the MITT population.

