**6.0 Study Visit Summaries:**

6.1 Screening Visit:

At this visit, the patient will be asked to provide written informed consent and inclusion and exclusion criteria will be evaluated to ensure that the patient meets all entrance criteria. See the Study Schedule of Activities section 7.17 for visit activities. After the informed consent process is complete, the subject will begin the run-in phase of the study.

Subjects may be enrolled if they are on a current Pentoxifylline regimen, but Investigators should not start patients on Pentoxifylline during the trial if the patient is not taking the drug at enrollment.

6.2 Run-in Visit:

There could be up to 4 visits during the run in phase, 3 visits if the Screening and Baseline visits occur on the same day. The visit schedule is as follows Screening/Baseline; Run-in Week 1 and Randomization ( $\pm 2$  days). The subjects will follow the treatment regimen outlined in section 7.17. At each visit the study staff will access the ulcer. If the subject meets any of the exclusion criteria listed in section 5.2.3 at the Randomization Visit the subject will be excluded from the study.

6.3 Randomization Visit:

At the randomization visit the subject will undergo procedures as outlined in the Study Schedule of Activities table in section 7.17.

The subject will leave the randomization visit with:

- Schedule for the next study visit (if possible, follow-up visits should be scheduled at the same time of day)
- Instructions on use and application of the assigned study apparatus, as applicable
- Diary and instructions to record daily activity
- Contact information and instructions to call if any problems arise

6.4 Treatment Visits (Weeks 1-16 or healed):

Investigational Group: Subjects will be seen in clinic at weeks 1, 2, 4, 6, 9, 12, 16 ( $\pm 2$  days) for 16 weeks or until the VLU is completely healed, as defined by complete closure with no open area or exudate. At the visits the subject will undergo the procedures as outlined in the Study Schedule of Activities table in section 7.17.

Control Group: Subjects will complete weekly visits for 16 weeks or until the VLU is completely healed, as defined by above. At the weekly visits the subject will undergo procedures as outlined in the Study Schedule of Activities table in section 7.17.

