The study staff will review the subject diary with the subject during each visit to ensure that all entries are complete and understood by the study staff. Any corrections must be made by the subject, and initialed and dated by them.

6.5 Support Contact:

Subjects randomized to the ACTitouch arm of the study will be contacted by study personnel (via text or phone call). The first follow up contact will occur 3 days ( $\pm 1$  day) after the Randomization Visit and the second follow up contact will occur 3 days ( $\pm 1$  day) after the Treatment Week 1 Visit.

For the remainder of the VLU treatment period, follow up contact will occur on weeks that the subject is not returning to the clinic for a study visit. The subject will be contacted during treatment weeks 3, 5, 7, 8, 10, 11, 13, 14, and 15 ( $\pm 2$  days from optimal date). If an ACTitouch subject is seen for an unscheduled study visit

within one of these windows, this will take the place of the support contact for that week.

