**6.6 Follow Up Visits (Months 1, 2 &3):**

Subjects who are assigned to the ACTitouch device and heal during the 16 week treatment period will continue to be seen monthly for 3 months ( $\pm 7$  days) post healed visit. At the visit the subject will undergo the procedures outline in the Study Schedule of Activities table in section 7.17.

The study staff will review the subject diary with the subject during each visit to ensure that all entries are complete and understood by the study staff. Any corrections must be made by the subject, and initialed and dated by them.

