**6.7 Unscheduled Study Visit:**

The subject may return to the investigational site for unscheduled visits during the study. At this unscheduled study visit the subject will complete all study procedures as outlined in the Study Schedule of Events Section 7.17.

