#### 12.6.2 Primary Endpoint Analysis:

The percentage of each subject's ulcer area reduction at 16 weeks will be assessed using a specialized ulcer camera and ulcer imaging system. Images will be centrally read by a qualified independent adjudicator. The percentage of ulcer area reduction for the ACTitouch® treated subjects will be compared with multi-layer bandaging treated subjects using analysis of covariance (ANOCOVA) with the following covariates: treatment group; duration of VLU ([1,6]; (6,24] months); baseline size of VLU, [1.5,12cm], (12,50cm]; history of diabetes; age. The analysis will be conducted on the ITT, MITT and Completer populations. The covariate adjusted one-sided lower bound 97.5% confidence interval of the treatment difference in mean percent ulcer area reduction (calculated as mean of ACTitouch® group minus mean of multi-layer bandaging treated group) is compared to the non-inferiority margin (-.125). If the lower bound exceeds the margin, the null hypothesis is rejected, and ACTitouch® system is deemed non-inferior to multi-layer bandaging.

A treatment-by-study center interaction will be assessed at the 0.10 level of significance using analysis of covariance with effects for treatment, study center and treatment-by-study center interaction. A non-significant interaction or any significant interaction deemed only quantitative in nature will not preclude study centers from being pooled for the final analysis. A significant qualitative interaction will be further inspected to

assess the study centers causing the interaction. Study centers with less than 15 subjects will be pooled by geographic region prior to carrying out the analysis.

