#### 12.7 Interim Analysis:

There will be a formal interim analysis of the primary endpoint when 50% of the subjects have completed the 16 week treatment phase, defined as completing all 16 weeks, healed or withdrew prior to the 16 week visit or healing. At this interim visit, comparison of the percentage ulcer area reduction between ACTitouch® treated subjects with multi-layer bandaging treated subjects will be made using the same ANOCOVA model as above. The DSMB will not recommend stopping the study for overwhelming efficacy based on the comparison of the ACTitouch® doses versus control (multi-layer bandaging). Nevertheless, due to the interim look, an O'Brien-Fleming-type alpha-penalty for the final analysis will be taken; and the final one-sided alpha will be 0.0249

The DSMB will be provided with conditional power of obtaining non-inferiority of ACTitouch to control with respect to mean percent ulcer healing by the end of the study. This conditional power is calculated according to the following formula:

$$CP_{\delta}(n_2, Z_{\alpha}|Z_1) = 1 - \Phi \left[ \frac{Z_{\alpha} \sqrt{2(n_1+n_2)} - Z_1 \sqrt{2n_1} - n_2(\delta - \delta_{\Delta})}{\sqrt{2n_2}} \right]$$

where:

$n_1$  – sample size per arm at interim;

$n_2$  – sample size per arm in second stage (from interim to final analysis) as originally planned;

$\Delta$  – non-inferiority margin;

$\delta_{\Delta} = \Delta/\sigma$  ;

$\sigma^2$  – assumption of true variance of treatment effects pooled across arms (estimated from the interim data);  
 $\delta$  – assumption of true effect size= $(\mu_C - \mu_T)/\sigma$  (this will be set to 0);  
 $z_1$  – non-inferiority test statistic calculated at the interim analysis;  
 $z_\alpha$  –  $\alpha$  percentile of the standard normal distribution ( $\alpha =$  one-sided 0.0249);  
 $z_\beta$  –  $\beta$  percentile of the standard normal distribution;  
 $\Phi[\ ]$  – the standard normal cumulative distribution function.

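### The Completer definition requires the week-16 visit, but treatment visits stop at healing, so it drops early healers and, at equal healing, drops more in control than in ACTitouch

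*Protocol*

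**What the plan says.** Protocol 12.5 defines the per-protocol (Completer) set as "All randomized subjects who have received the investigational procedure per protocol and who completed the 16 week follow-up visit". No clause admits a subject who healed earlier. Protocol 12.6.2 uses this set for the non-inferiority comparison: "The analysis will be conducted on the ITT, MITT and Completer populations". Protocol 12.5 names MITT as primary. SAP 8.3 and 8.3.1 use ITT for the primary analysis, but SAP 8.3.2 keeps all three populations for the Charing Cross analysis.

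Protocol 6.4 gives the arms different clinic schedules. For ACTitouch: "Subjects will be seen in clinic at weeks 1, 2, 4, 6, 9, 12, 16", for 16 weeks or until complete healing. For control: "Subjects will complete weekly visits for 16 weeks or until the VLU is completely healed, as defined by above". Between clinic visits ACTitouch subjects have a text or phone contact (Protocol 6.5): "The subject will be contacted during treatment weeks 3, 5, 7, 8, 10, 11, 13, 14, and 15". After healing, scheduled visits exist in the device arm only. Protocol 6.6 says that ACTitouch subjects who "heal during the 16 week treatment period will continue to be seen monthly for 3 months".

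**The concern.** Someone whose ulcer is seen closed at week 8 has finished treatment visits under 6.4 and has no week-16 treatment visit. Under 12.5 that person is not a Completer, although the outcome is the best one possible. The Completer analysis therefore loses most of its healed subjects.

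The loss also depends on how often each arm is examined. Healing after the week-12 visit and by week 15 is picked up in control at weeks 13 to 15, so the subject is dropped. The same healing in ACTitouch has no scheduled visit to record it until week 16, where it is kept as 100% reduction. At equal healing this favours the device, which is the anti-conservative direction for non-inferiority.

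The Completer result is the protocol's per-protocol check on the non-inferiority claim. As defined, it can differ from the MITT or ITT result because of the visit calendar alone.

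**Working it through.** The plan states no figure for this effect, so there is none to reproduce.

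**Schedule check.** Weeks 1 to 16 without the ACTitouch clinic weeks (1, 2, 4, 6, 9, 12, 16) leave 3, 5, 7, 8, 10, 11, 13, 14 and 15. These are exactly the support-contact weeks in Protocol 6.5. No ACTitouch clinic visit is scheduled in weeks 13 to 15.

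**Inputs from the documents.** Visit weeks (6.4), 102 per arm (Synopsis), margin -0.125 (12.6.2).

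**Assumed inputs.** Share healed by week 16, *H*; mean reduction in unhealed ulcers, *r*; constant healing hazard; no withdrawals; share *u* of ACTitouch healing between the week-12 visit and week 15 that an unscheduled visit records before week 16.

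**Formulas.**
- Healed by week *t*: F(t) = 1 - (1 - H)^(t/16)
- Dropped share, control: F(15)
- Dropped share, ACTitouch: F(12) + u[F(15) - F(12)]
- Completer mean: [(H - dropped) × 1 + (1 - H) × r] / (1 - dropped)

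**Equal arms, H = 0.5, r = 0.4, u = 0.**
- Control: F(15) = 1 - 0.5^0.9375 = 0.478, or 48.7 of 102 (about 49 of 51 healers). Mean = (0.022 + 0.200)/0.522 = 0.425.
- ACTitouch: F(12) = 1 - 0.5^0.75 = 0.405, or 41.4 of 102 (about 41 of 51 healers). Mean = (0.095 + 0.200)/0.595 = 0.495.
- Difference: +0.070. The true mean is 0.5 × 1 + 0.5 × 0.4 = 0.70 in both arms, so the true difference is 0.

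A simulation with the actual visit weeks and 2,000,000 subjects per arm gave dropped shares of 0.478 and 0.406 and the same +0.070.

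**Sensitivity, equal arms.**

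| Case | Completer difference (points) |
|---|---|
| H 30–70%, r 20–60%, u = 0 | +2.5 to +15.0 |
| H 50%, r 40%, u = 25%, 50%, 75%, 100% | +5.4, +3.7, +1.9, 0 |
| H 30–70%, r 20–60%, u = 50% | +1.3 to +8.3 |
| H 50%, r 40%, u = 0, later healing (Weibull shape 2; dropped 45.6% control, 32.3% ACTitouch) | +10.9 |

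**Unequal healing, r = 0.4 in both arms, u = 0.** True difference = 0.6 × (difference in H).

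| Healed, ACTitouch v control | True (points) | Completer (points) |
|---|---|---|
| 45% v 55% | -6.0 | +5.4 |
| 39.5% v 60.5% | -12.6 | +3.7 |
| 55% v 45% | +6.0 | +8.7 |
| 60% v 40% | +12.0 | +10.4 |

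In the second row the device is worse by slightly more than the margin, yet the Completer point estimate favours it. In the last row the error goes against the device.

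**The case against.** The strongest reply is that early healers were plainly meant to count. Protocol 12.7 treats healing as finishing the treatment phase ("defined as completing all 16 weeks, healed or withdrew prior to the 16 week visit or healing"), 7.9 sends the healed-visit image to the adjudicator, and 12.3.3 and 12.6.4 analyse healing, ulcer-free days and cost at 16 weeks, which presupposes a week-16 status for early healers. As evidence of intent this stands. It does not change membership under 12.5: the 12.7 wording governs interim timing only, and it also counts withdrawals, so it cannot serve as the Completer definition.

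Second, the schedule-of-activities table and the full SAP are not visible in the public text, and either might treat the healed visit as the week-16 visit. That stands and limits confidence.

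Third, the arms may differ less than shown. Protocol 6.7 says "The subject may return to the investigational site for unscheduled visits during the study", and the support contacts in weeks 13 to 15 could prompt one. This narrows the gap and closes it only if all such healing is caught; even then both arms lose nearly all their healers. If instead a post-healing visit near week 16 counted as the week-16 visit, only ACTitouch healers have one scheduled, which would widen the gap.

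Fourth, Completers are not the primary population, no SAP efficacy table shell is labelled for them, and no effect on the Charing Cross score has been estimated. All correct; this bears on severity.

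**Conclusion.** The concern holds as the protocol is worded. Subjects seen healed before week 16 fall outside the Completer set, and at equal healing control loses more of them. That direction needs only some healing between the week-12 visit and week 15 that no unscheduled ACTitouch visit records.

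The size rests on assumed healing rates, unhealed means and hazard shape. Under the central assumptions it is +7.0 points toward the device, with a constant-hazard range of +2.5 to +15.0, falling to 0 if unscheduled visits catch everything. If true healing differs between arms, the error can go either way. These figures illustrate the mechanism and are not a forecast.

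The protocol's MITT and the SAP's ITT primary populations are unaffected by this wording. The effect falls on the protocol's Completer analyses and on the SAP 8.3.2 analysis in all three populations. Protocol 12.6.2 ties missing data to premature withdrawal, and 5.2.4 does not list healing as withdrawal. The complete-case analysis and the SAP's available-case tables are therefore affected only if read as needing a week-16 measurement. This should be fixed, but it does not undermine the primary analysis.

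**What to change.** In Protocol 12.5, define Completers as subjects treated per protocol who either completed the week-16 visit or had adjudicated healing before it. In Protocol 12.6.2 and SAP 8.3.1, score adjudicated healing at or before week 16 as 100% reduction at week 16, by the same rule in both arms and in every analysis set, including the complete-case and available-case sets. Do not replace that score with a post-healing area in the main analysis, since only ACTitouch healers have scheduled post-healing visits. Report re-opening separately.

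Under this rule the equal-arm illustration gives 0.70 in both arms and a difference of 0, whatever the visit schedule.

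The cost is one clause in 12.5 and one scoring sentence in each of 12.6.2 and SAP 8.3.1. The healed-visit image is already adjudicated under 7.9, so the area score needs no new visit or image. There are two consequences to accept. Re-opening before week 16 is not counted in the primary score, which is a choice about what the endpoint measures and should be stated as such. The Charing Cross analysis also needs its own stated value for early healers, which the area rule does not supply.

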#### 12.6 Analysis Plan:

##### 12.6.1 General Analysis Issues:

Statistical analysis will be performed using SAS Version 9.4 or higher. Non-inferiority analyses will be considered statistically significant at the

one-sided  $\alpha=.025$  level. All other p-values presented will be two-sided and will be considered statistically significant at the two-sided  $\alpha=.05$  level of significance unless otherwise noted. Statistical testing of the primary and secondary endpoints (Stage I) will be performed in hierarchical fashion. The primary efficacy analysis will be performed at the one-sided  $\alpha=.025$  level. If the primary efficacy analysis is statistically significant then the first secondary end point will be analyzed at the two-sided  $\alpha=.05$  level. If this analysis is statistically significant, then the second secondary end point will be analyzed at the two-sided  $\alpha=.05$  level. Otherwise, testing on secondary endpoints will cease and the treatment will not be considered beneficial on either secondary endpoint. P-values for exploratory endpoints will not be adjusted for multiple comparisons.

Baseline demographic and background variables will be summarized by treatment group and strata. For categorical variables, frequencies and percentages will be presented. For continuous variables, descriptive statistics including: sample size, mean, standard deviation, minimum, and maximum, will be presented. Continuous variables will be compared between treatment and control groups using ANCOVA. Categorical variables will be compared between treatment and control groups using the Kruskal-Wallis tests.

#### 12.6.2 Primary Endpoint Analysis:

The percentage of each subject's ulcer area reduction at 16 weeks will be assessed using a specialized ulcer camera and ulcer imaging system. Images will be centrally read by a qualified independent adjudicator. The percentage of ulcer area reduction for the ACTitouch® treated subjects will be compared with multi-layer bandaging treated subjects using analysis of covariance (ANOCOVA) with the following covariates: treatment group; duration of VLU ([1,6]; (6,24] months); baseline size of VLU, [1.5,12cm], (12,50cm]; history of diabetes; age. The analysis will be conducted on the ITT, MITT and Completer populations. The covariate adjusted one-sided lower bound 97.5% confidence interval of the treatment difference in mean percent ulcer area reduction (calculated as mean of ACTitouch® group minus mean of multi-layer bandaging treated group) is compared to the non-inferiority margin (-.125). If the lower bound exceeds the margin, the null hypothesis is rejected, and ACTitouch® system is deemed non-inferior to multi-layer bandaging.

A treatment-by-study center interaction will be assessed at the 0.10 level of significance using analysis of covariance with effects for treatment, study center and treatment-by-study center interaction. A non-significant interaction or any significant interaction deemed only quantitative in nature will not preclude study centers from being pooled for the final analysis. A significant qualitative interaction will be further inspected to

assess the study centers causing the interaction. Study centers with less than 15 subjects will be pooled by geographic region prior to carrying out the analysis.

A qualitative interaction between center and treatment group is defined as directionally inconsistent estimated coefficients for the treatment group parameter in a subgroup analysis of treatment group by center – i.e., analysis of covariance model with stratification by center specified as subgroups. Any study center with a qualitatively different treatment group effect by subgroup will be compared with other centers in terms of a number of variables including: enrollment rate, adverse event rate, rate of data queries generated by clinical data management, confirmation of correct drug assignment and randomization at the site, number and seriousness of protocol deviations. If a center is deemed to be qualitatively different from the other centers in terms of their interaction with treatment group, then the primary efficacy analysis will be stratified by center (i.e., those centers with a qualitative a difference versus all others). If only one or two centers are qualitatively different, then analyses will be conducted with and without the centers, and the results will be compared.

Several imputation approaches will be used for missing data due to subjects prematurely withdrawing prior to the 16 week time point. The results will be descriptively compared across approaches to assess the sensitivity of results to the various techniques.

- Complete case analysis
- Multiple imputations via the linear regression technique, where the imputation model will include treatment group and all covariates discussed in the Analysis Plan.
- Available data analysis (include any available measurements) using the general linear mixed models.

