
Efficacy [If applicable]
	
Group 1: Multi-Layer Bandage
 
 
• Will be seen in clinic once per week for: 
 
○ Wound assessment
 
○ wound dressing changes, debridement, if necessary, as determined by the treating study investigator
 
○ wound tracing; photo
 
○ limb volume measurements
 
 
 
• Subjects will be instructed to wear the MLB 24 hours daily, except upon removal and re-application during weekly clinic visits with debridement as determined necessary by PI
 
 
Group 2: ACTitouch Adaptive Compression System
 
 
• Will be seen in the clinic at weeks 1, 2, 4, 6, 9, 12, 16 during the treatment period. Subjects who experience complete healing of the study VLU will return to the investigational site 1, 2 and 3 months post heal. 
 
○ wound assessment, as applicable
 
○ wound dressing changes, debridement, if necessary, as determined by the treating study investigator
 
○ wound tracing; photo, as applicable
 
○ limb volume measurements
 
 
 
• Subject will be instructed to wear the AT in sustained mode for a minimum of 12 hours per day plus 2 hours IPC mode.
 

Safety
	
Adverse event monitoring  Subject interview  Physical examination

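### As described, the multiple imputation in Protocol 12.6.2 repeats the complete-case analysis; only the mixed model can use ulcer areas measured before dropout, and no approach departs from missing-at-random

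*Protocol*

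**What the plan says.** Protocol 12.6.2 opens its missing-data text with "Several imputation approaches will be used for missing data due to subjects prematurely withdrawing prior to the 16 week time point". It then lists three approaches:

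- "Complete case analysis";
- multiple imputation by linear regression, for which "the imputation model will include treatment group and all covariates discussed in the Analysis Plan";
- a third approach based on mixed models, given as "Available data analysis (include any available measurements) using the general linear mixed models".

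The stated purpose is a sensitivity comparison: "The results will be descriptively compared across approaches to assess the sensitivity of results to the various techniques". The covariates of the primary model, in the same section, are "treatment group; duration of VLU ([1,6]; (6,24] months); baseline size of VLU, [1.5,12cm], (12,50cm]; history of diabetes; age". No ulcer area measured after randomization is named as a covariate anywhere in 12.6.

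Those areas will exist. Protocol 7.9 has the study ulcer photographed and traced at each visit. The Synopsis says of the ACTitouch group "Will be seen in the clinic at weeks 1, 2, 4, 6, 9, 12, 16 during the treatment period", and Protocol 6.4 has the bandaging group seen weekly. In both arms the visits stop once the ulcer has healed.

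The abbreviated SAP (8.3.1) names a linear mixed model ANCOVA on the ITT population with the same covariates. It does not mention multiple imputation, and the shell of Table 14.2.3 shows baseline and week 16 only.

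**The concern.** A sensitivity comparison is informative only if the approaches can disagree. An imputation model built from the analysis covariates gives a subject who withdrew the value expected for someone of the same arm, ulcer class, diabetes status and age. It ignores whether that subject's ulcer was shrinking or growing when last traced. Agreement between this imputation and complete case is then guaranteed by construction and says nothing about dropout.

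This matters more than usual here. The trial is open label and tests non-inferiority, and Protocol 5.2.4 allows exit by subject choice, by investigator decision, for an adverse event, or after an over-long treatment pause for infection. Such exits can follow poor response and can differ by arm. If poor responders leave the device arm selectively, complete case and the imputation as written both favour the device.

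**Working it through.** **Scale.** Differences are ACTitouch minus bandaging, as proportions; 0.01 is one percentage point and the margin is -0.125 (Protocol 12.6.2).

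**Inputs from the documents.** 204 subjects, 102 per arm (12.1); one-sided alpha 0.025 (12.6.1); the covariates of 12.6.2; the visit schedule in the Synopsis and 6.4.

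**Assumed inputs.** The public text gives no SD, power, dropout rate or correlation between early and week-16 reduction. Solving the usual non-inferiority formula for the SD that 102 per arm supports with no dropout gives 0.125 × √(102/2) / (1.960 + 0.842) = 0.319 at 80% power, or 0.125 × √(102/2) / (1.960 + 1.282) = 0.275 at 90%. The simulation used SD 0.32 and correlation 0.5 or 0.7.

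**Step 1: algebra.** Let X hold the intercept, treatment and the baseline covariates, and let b be the least-squares fit in subjects with week-16 data. The normal equations give X_obs′y_obs = X_obs′X_obs b. Imputed values are X_mis b* plus residual noise, with b* drawn around b. Averaged over draws, the fit to the completed data is

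(X′X)⁻¹ [X_obs′X_obs b + X_mis′X_mis b] = b.

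The pooled treatment effect is therefore the complete-case effect plus Monte Carlo noise. This holds for any dropout rate, SD or dropout mechanism.

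**Step 2: simulation, true difference 0.** 102 per arm, 600 trials per row, 100 imputations. Control dropout was completely random at 10%, 20% or 30%. Device-arm dropout rose with poor early response.

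| Missing overall | Correlation | Full data | Complete case | Imputation as written | Imputation with one early area |
|---|---|---|---|---|---|
| 12.4% | 0.5 | 0.0030 | 0.0271 | 0.0273 | 0.0031 |
| 12.3% | 0.7 | 0.0006 | 0.0334 | 0.0334 | 0.0003 |
| 22.8% | 0.5 | -0.0010 | 0.0396 | 0.0396 | 0.0004 |
| 22.4% | 0.7 | 0.0027 | 0.0563 | 0.0564 | 0.0023 |
| 32.0% | 0.5 | -0.0008 | 0.0524 | 0.0525 | 0.0017 |
| 32.1% | 0.7 | -0.0026 | 0.0681 | 0.0680 | -0.0027 |

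With equal arms, device-arm missingness runs from about 2 × 12.4 - 10 = 14.8% to 2 × 32.1 - 30 = 34.2%. Complete case and the imputation as written agree within 0.0002 on average, and their standard errors within 0.0005. In one simulated trial with 10,000 imputations they gave 0.00104 (SE 0.04181) and 0.00121 (SE 0.04182).

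Complete-case bias runs from 0.0271 - 0.0030 = 0.024 to 0.0681 + 0.0026 = 0.071, which is 19% to 57% of the margin. Adding one early area removes it.

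**Step 3: type I error.** True difference -0.125, correlation 0.7, 1500 trials, 40 imputations:

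| Control dropout setting | Complete case | Imputation as written | With early area |
|---|---|---|---|
| 20% | 0.191 | 0.189 | 0.025 |
| 30% | 0.271 | 0.273 | 0.026 |

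**Step 4: the third approach, and the reverse direction.** A likelihood-based repeated-measures model using weeks 6 and 16 was run under milder dropout (about 15-17% missing on the device, 7-9% on bandaging; SD 0.32, correlation 0.5 or 0.7; 4000 trials per scenario; true difference 0). Complete case gave +0.008 to +0.016 and the mixed model -0.0005 to +0.0009. With the dropout pattern reversed between arms, complete case gave -0.009 to -0.015.

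**The case against.** **The plan already has an approach that uses earlier areas.** This stands, and it sets the limit of the point. A reader might infer that the plan has no real sensitivity check, or that agreement across all three approaches is bound to be falsely reassuring. The documents do not support that: a mixed model fitted to every visit would depart from the other two in just the situation of concern (step 4). What remains is that its visits and terms are not stated. If fitted to week 16 alone, as the shell of Table 14.2.3 could suggest, it would have one outcome per subject and would also rest on complete cases.

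**To include is not to include only.** This is fair as a reading, and 12.6.2 also discusses study center. Adding center would break the exact equality slightly but would bring in no response after randomization. The SAP supplied is abbreviated and refers to an original that is not among the documents, so auxiliary variables may be named there. The point concerns the imputation as the available text describes it.

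**The direction is not established.** This also stands. A reader might infer that the primary result will be biased towards non-inferiority. The Protocol's background (3.1) presents the device as better accepted than bandaging, which could make response-related exits heavier on bandaging; the bias would then count against the device.

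**Interim tracings are not adjudicated.** Protocol 7.9 names only the initial, enrollment and healed images for the independent adjudicator. Interim areas therefore appear to be open-label site tracings. They can serve as auxiliary predictors but not as outcomes.

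**Conclusion.** The point holds in a limited form. With the covariates listed in 12.6.2 and only the week-16 outcome missing, multiple imputation and complete case are effectively one analysis; that is algebra and needs no assumption about dropout. The mixed model is the only listed approach that can use pre-dropout areas, and only if it is fitted to them. None of the three tests a departure from missing-at-random.

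The size is conditional. Under the assumed SD of 0.32 and correlation of 0.5 to 0.7, the shared bias was about 2 to 7 points when device-arm dropout followed poor response at roughly 15% to 34%, and about 1 to 2 points in the milder setting. The sign reverses if such dropout is heavier on bandaging. These figures illustrate what the comparison could miss; they do not predict this trial's result. The change is worth making before the data are analysed, because it is nearly free and removes a later choice in an unblinded trial.

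**What to change.** In Protocol 12.6.2 and the SAP:

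1. Name ulcer area, or percent reduction, at the visits scheduled in both arms (weeks 1, 2, 4, 6, 9 and 12) as auxiliary predictors in the imputation model, and impute separately by arm.
2. Count subjects who healed and stopped visits as 100% reduction at week 16, not as missing, and say how their later areas enter the model.
3. Do not simply cap normal draws at 100%. With an imputed mean of 0.7 and SD of 0.25 to 0.32, capping lowers the mean by 1.4 to 3.0 points per imputed value. Check that shift, or use a bounded method such as predictive mean matching.
4. State that the mixed model uses all treatment visits with a treatment-by-visit term, and estimate the week-16 difference from it.
5. Add one delta-adjusted run that lowers imputed ACTitouch values by up to the 12.5-point margin. At the full shift this moves the estimate by about the device-arm missing fraction times 12.5: 0.15 × 12.5 = 1.9 points, or 0.34 × 12.5 = 4.3 points.
6. Reconcile the Protocol with the abbreviated SAP on which missing-data analyses will be reported, since the SAP lists no imputation output.

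The cost is some extra programming and a few sentences of text, with no new data. The limitation is that the interim areas appear to be unadjudicated and should be used as auxiliary predictors only.
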